## **Exposure Day**

In order to participate in this study, subjects will be required to:

- Avoid smoke and fumes for 24 hours before all visits.
- Avoid drinking alcohol 24 hours before all visits.
- Avoid strenuous exercise for 24 hours prior to and after all visits.
- Refrain from eating pan fried and/or grilled foods after midnight prior to the exposure day.
- Refrain from ingesting caffeine for 12 hours prior to all study visits.
- Eat a light breakfast on the exposure day.
- Bring a lunch to each exposure day. The lunch composition will be specified to minimize potential variations that could affect the arterial diameter measurements. Subjects will be compensated for the cost of the lunch.

**Pre-exposure:** On the day of the study, the subject will report to the medical station in the HSF at which time the general health of the subject will be evaluated and the appropriate pre-exposure measurements (blood pressure, HRV, endothelial cell function by brachial artery ultrasound (BAU), pulmonary function by spirometry and diffusion limited uptake of CO (DLCO), and blood sampling) will be completed.

- **HRV measurement** will be done with the use of a Holter monitor. Electrodes for HRV measurement will be placed. The skin in the areas of electrode placement will be cleaned and shaved (if necessary) to ensure that the electrodes will remain securely attached. These leads will be connected to a Holter monitor and will remain in place for approximately 48 hours. Standard telemetry leads will also be placed, and removed when the patient leaves for the day. The subject will then be allowed to relax for 20-30 minutes in a reclined position.
- **Brachial artery ultrasound.** Brachial artery ultrasound (BAU) to evaluate flow-mediated dilatation will be performed using a 14 MHz imaging probe interfaced with an Ultrasonix SP or Touch Pharma ultrasound machine. The diameter of the brachial artery will be measured at baseline, during reactive hyperemia and after administration of sublingual nitroglycerin. The subject will lie supine, and a pneumatic tourniquet will be placed around the right upper arm proximal to the target artery. Gated baseline images of the brachial artery will be acquired after 15 minutes of supine rest. The pneumatic cuff will then be inflated to a pressure of 200 mm Hg for 5 minutes, and increased flow will be induced by sudden cuff deflation. A second scan will be performed following deflation. The subject will rest another 10 minutes and a third ultrasound scan will be performed. Sublingual nitroglycerin (~0.4 mg) will be administered, followed in three to four minutes by the final ultrasound study. Subjects will then rest quietly for 5 minutes. Images of the brachial artery will be acquired and stored on a personal computer, and subsequently analyzed using a semi-automated offline quantification system.
- **Pulmonary function:** will be measured by spirometry, including measurement of single breath CO diffusing capacity ( $D_LCO$ ). Cardiac output ( $Q_c$  or pulmonary capillary flow) will be simultaneously measured from the uptake of inhaled acetylene gas during the same single breath procedure.
- **Blood sampling:** approximately 46.2 ml of blood will be collected pre-exposure in the study.

- *Symptom questionnaire* before and after exposure may be collected.
- **Blood Pressure Monitor:** An ambulatory blood pressure monitoring device will be placed on the subject's arm and begin collecting readings. Subjects will wear the blood pressure monitor and cuff for the rest of the day after leaving the facility but will be instructed to remove it before going to bed.

**Exposure:** All exposures will be carried out at the EPA Human Studies Facility on the UNC campus. Subjects will enter an exposure chamber for the 2-hour exposure to clean air. The next day they will undergo exposure to fine/ultrafine CAP for 2 hours. The CAP exposure day may be rescheduled if the particulate concentrations are too low on the scheduled day.

The actual concentration of CAP will be determined retrospectively by filter gravimetry, with exposures monitored in real time with a tapered element oscillating microbalance (TEOM). Subjects will be monitored continuously by the EPA personnel by closed-circuit camera, blood pressure measurements, pulse oximetry and ECG telemetry. A duty physician will be available at all times. The subjects will be able to end their exposure and exit the chamber at any time if they choose to end their participation in the study. Blood pressure, heart rate, and oxygen saturation will be measured continuously during the exposure period. A confirmed blood O2 saturation levels less than 89 % will result in a cessation of exposure. Heart rate alarm limits will be set up for each subject and monitored continuously by the console operator and the nursing staff.

**CAP Exposures-**Concentrated particles will be generated by drawing ambient air from above the roof of the Human Studies Facility and passing the air through a 2 stage aerosol concentrator which produces up to a 20-fold increase in particle number and mass. Particles larger than about 2.5 microns will be excluded by a size-selective inlet from entering the concentrator at the rooftop intake. During the particle concentrating process, ambient air pollution gases will be diluted by a factor of four. Air temperature and humidity will be monitored and maintained to ensure proper operation of the concentrator. An air conditioner in the chamber can be utilized to both heat or cool chamber air for subject comfort. The flow of air into the chamber will be 65 liters per minute, with approximately 15 liters per minute diverted for analytical instrumentation and filter devices attached upstream from the chamber. The remaining approximately 50 L/min will be provided to the subject through a face mask. Since the air will be pulled into the chamber by a suction blower connected downstream of the chamber, the chamber will be slightly below atmospheric pressure.

The concentration of particles delivered to the chamber will vary depending on the levels of naturally occurring particles in the Chapel Hill air. Although 24 hr averages seldom exceed 15-20 ug/m^3, peak values in the summer can be as high as 50-60 ug/m^3 with lower values during the rest of the year. A face mask is used to reduce the daily and seasonal variability of PM concentration. Our past experience provides a basis to expect the particle mass delivered to the mask will be up to 600 ug/m^3. The particle burden, on a mass basis presented to the volunteer will not exceed an exposure an individual receives over a 24 hour period while visiting a typical urban center in America on a smoggy day. The particle mass of the outdoor air entering and exiting the aerosol concentrator will be monitored continuously. Filter samples will be obtained from the devices located upstream from the chamber and analyzed for both mass and chemical composition of particles. If it is confirmed that particulate mass levels exceed 600 ug/m^3 for greater than 6 minutes, exposure will be terminated. The process for confirmation may take up to

additional 10 minutes. The shutdown procedure involves venting a valve on the exposure chamber, which markedly reduces the particle exposure, and alerting the investigator with both auditory and visual signals leading to removal of the subject from the chamber. Blood pressure, telemetry, and oxygen saturation will be measured during the exposure period.

**Immediate Post-exposure:** Subjects will be released while wearing the Holter and blood pressure monitors. Symptoms questionnaire after exposure will be collected. Blood pressure, lung function, endothelial cell function, and heart rate variability will be measured and approximately 46.2 ml of blood samples will be collected.

**Eighteen Hours Post-PM exposure:** Eighteen hours after the exposure, the subjects will return to the HSF to undergo a brief medical evaluation, including blood pressure, spirometry (pulmonary function testing) and endothelial cell function (BAU) measurements. The subject will then be allowed to relax for 20-30 minutes in a reclined position, after which a 10-minute resting HRV measurement will be obtained, and approximately 46.2 ml of blood will be taken. Holter monitor will be removed.

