## Subject Qualification

**Screening:** Subjects will be recruited by the Westat Corporation (see section B1 below). During an initial telephone interview, the subjects will receive information regarding the study and their eligibility status will be assessed. Subjects whose responses indicate that they are likely to meet the criteria will be scheduled for a genetic screening appointment in the medical station in the US EPA Human Studies Facility (HSF). Depending on the need to maintain a representative population of subjects over time, GSTM1 null or sufficient subjects may be enrolled exclusively at various points in the study. At that time a genotype screening informed consent form and a consent form for storing blood with identifying information will also be signed. The subjects identified from a previous study (see page 26, methods of recruiting) will not need genotype screening. Subjects will then undergo a brief medical history screening and blood pressure measurement. Subjects will then have approximately 20 ml of blood collected. A portion of the blood will be used for genetic screening for GSTM1 sufficiency and another portion of the blood will be used for the cholesterol levels, fatty acid analysis, and biochemistry analysis. Information obtained from the blood analyses at this point could be used by the study physicians to stop a subject's participation or end the study. Subjects will be given a copy of the Medical History Form to be filled out and mailed back after they are selected on the genotype.

**GSTM1/GSTP1 genotype screening:** A portion of the blood sample (about 5 ml) will be used for genotyping of GSTM1 and other non-selective genotypic markers such as GSTP1. Total DNA will be isolated from the blood sample and polymeric chain reaction (PCR) will be run to determine if the subject carries a GSTM1 positive or null gene polymorphism.

**Physical exam:** Subjects who are not excluded during the genetic screening will be scheduled for a physical examination in the HSF. During this visit, subjects will sign an informed consent to undergo the screening procedures and physical examination as per the previously UNC IRB-approved protocol, Recruitment and Screening of Potential Participants for U.S. EPA Studies (95-EPA-66). Subjects will then undergo a physical exam, pulse oximetry, and screening/baseline 12-lead electrocardiogram (ECG). A menstrual history will be collected on all female subjects.

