#### **OUTCOMES:**

**Pulmonary Function** will be measured before and after exposure. Subjects who have recent abdominal and/or eye surgery or any type of hernia will not be tested for pulmonary function. Subjects will perform spirometry and single breath diffusing capacity (DLCO) on a Sensor Medic Vmax pulmonary function system according to the standard procedure published by the American Thoracic Society. In addition, regional DLCO and pulmonary capillary blood flow (Qc) will be obtained by the intrabreath technique using the same system.

**Heart Rate Variability (HRV)** data will be gathered for 24 hours using a Holter monitor. Specific 10 minute epochs to be analyzed for frequency domain variables include times immediately prior to exposure, immediately following exposure, and approximately 24 hours after exposure. Both time and frequency domain variables will be analyzed, as will abnormal responses (e.g. premature atrial complex, premature ventricular contractions, bradycardia, and tachycardia).

**Flow-Mediated Dilatation (brachial artery ultrasound).** Changes in diameter of arteries caused by reactive hyperemia (endothelium-dependent vasodilatation) and by administration of sublingual nitroglycerin, typically 0.4 mg, (endothelium-independent vasodilatation) will be expressed as a percent change in diameter relative to resting baseline values.

**Peripheral Venous Blood Sample.** Approximately 50 ml of venous blood will be drawn before, immediately after (within 1 hr after exposure ends), and approximately 18 hrs after exposure (Please refer to Table 1 in this section). The site will be prepared with isopropyl alcohol and a tourniquet is applied. Blood is drawn from an antecubital or other appropriate vein. Endpoint measurements will include, but are not limited to the following: blood lipid omega-3 fatty acid levels, biomarkers for specific and non-specific immune responses, coagulation factors, vasoactive factors, and soluble components of PM (e.g. transition metals).

Genotype Screen	Air Exposure	Ozone-Exposure	Follow-up	TOTAL
20	46.2/46.2	46.2/46.2	46.2	251 ml

Table 1. Blood Draws

Our primary endpoints will be HRV measurement, pulmonary function and peripheral venous blood markers. Our secondary endpoints will be arterial wall function and pulmonary function measurements.

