- **Confidentiality** Risk of breach of confidentiality is minimal. All subjects will be assigned a study number which will be used for data recording – not the subject’s name. The study number is all that will be entered into computer databases. All paper files that may contain the subject’s name or screening number are secure in the EPA building that has limited access 24 hours/day. Any abnormal medical findings (CBC, ECG, brachial artery ultrasound image, spirometry) will be discussed with the volunteer and the volunteer will be counseled to seek treatment from his/her personal physician if indicated. Samples will be stored at the U.S. EPA HSF. A numeric coding system will be used to ensure that subjects cannot be directly identified from the samples alone.

**A.4.8. Data analysis.** Tell how the qualitative and/or quantitative data will be analyzed. Explain how the sample size is sufficient to achieve the study aims. This might include a formal power calculation or explanation of why a small sample is sufficient (e.g., qualitative research, pilot studies).

To test our hypothesis that CAP causes adverse cardiovascular effects in GSTM1 null older human volunteers, we will measure a number of relevant endpoints, including blood pressure, HRV, brachial arterial blood flow rate, change in blood coagulation factors, platelets, fibrinogen, c-reactive protein, lactate, plasminogen activator inhibitor, ferritin, and  $\alpha$ 1-antitrypsin. In this study, our primary endpoints will be HRV measurement and peripheral venous blood markers. Our secondary endpoints will be endothelial cell function and pulmonary function measurements. Statistical data analyses will consist of ANOVA for continuous variables and rank sum tests for non-continuous variables pre- and post-exposure. A  $p$  value of 0.05 or less will be considered significant.

The sample size was calculated to detect a difference of 10% change in HRV assuming a standard deviation of 9%. Using GraphPad software, an N of 15 was derived using a power of 0.8 and an  $\alpha$  of 0.05. This study will enroll approximately 30 subjects in order to provide sufficient power to all for the examination of differences between GSTM1 null and positive subjects.

The study cohort will be monitored through genetic screening to ensure that individuals with GSTM1 null genotype are represented in a proportion approximately equal to the prevalence in the US population, about 40%.

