1. If following genotyping of the blood samples on screening day, it is determined that the individual's genotype is not needed for completion of the study, then that subject may be informed that his/her participation in this study is no longer necessary. The subject will be notified by phone and the total compensation for this study will be approximately \$30.
2. If the subject is qualified and finishes the entire study, the total compensation for completion of this study will be approximately \$1857.

Pre-study qualifications (screening+blood+physical)	\$60
Training day (3 hours) + Dietary recording	\$200
Exposure Day Time and Procedures (includes \$5 for lunch)	(\$603/day)
Total:	\$1206
Follow- up Day Time and Procedures	
Total:	\$141
On-Time Bonus	\$50
Dietary Compliance	\$100
Study Completion Bonus	\$100

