## APPENDIX B

## CAPTAIN EQUIPMENT AND CONFIGURATION

## Study Summary

Number of subjects:	200 recruited/30 complete
Locations:	Chamber AC89, Chamber PC89, Test Room TB87, Medical Station
Exposures per subject:	Two 2-hour exposures using face mask – first to clean air; second to concentrated fine/ultrafine particles (preferably $>50 \mu\text{g}/\text{m}^3$ )
Study blind status:	N/A

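### Outcome reading is nowhere masked, although the stored brachial-artery images, and with some preparation the Holter epochs, could cheaply be read without knowledge of session or genotype

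*Protocol*

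**What the plan says.** **Reading of images.** Protocol A.4.5 (Exposure Day, Brachial artery ultrasound) has the images stored on a computer and "subsequently analyzed using a semi-automated offline quantification system". The reader is not named, and nothing is said about what the reader is told.

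**Reading of Holter data.** The leads "will remain in place for approximately 48 hours" (Exposure Day, HRV measurement). Under OUTCOMES, "Specific 10 minute epochs to be analyzed for frequency domain variables include times immediately prior to exposure", as well as times immediately after and about 24 hours after exposure. Ectopic beats, bradycardia and tachycardia are also analysed.

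**Blinding.** The one entry is "Study blind status" in Appendix B of the contractor's Protocol Operations Plan, filled in as N/A. The IRB application (Parts A and B) does not mention masking of exposure, genotype or readers.

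**Session.** Operations plan section 2.0 fixes the sequence for everyone: clean air on Tuesday in Chamber PC89, CAP on Wednesday in Chamber AC89.

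**Genotype.** It is determined at screening and acted on. Under Subject Qualification, "GSTM1 null or sufficient subjects may be enrolled exclusively at various points in the study". Under B.6, a subject may be released when the "genotype is not needed for completion of the study".

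**Coding.** A.4.7 (Confidentiality) says "All subjects will be assigned a study number which will be used for data recording". This replaces the name.

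**Endpoint rank.** A.4.8 makes HRV and blood markers primary, and endothelial and pulmonary function secondary.

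**The concern.** Subjects and chamber staff can hardly be masked to which of two chambers is in use, and that may be why blinding was treated as not applicable. The argument does not extend to measurements taken later from stored data. A semi-automated measurement leaves some input to an operator, and Holter analysis normally involves some beat editing, although the protocol does not describe it.

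The hypothesis in A.4.8 is directional: CAP is expected to do harm in GSTM1-null subjects. If a reader knew that a scan was post-CAP in a null subject, small choices of frame, edge correction or beat exclusion could lean that way. Pairing each subject with their own air session would not remove such a shift, because the shift would itself depend on session and genotype. The problem is also separate from the confounding of exposure with day and chamber: randomising the order would not mask the readers.

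This belongs in the protocol because it concerns conduct. A later analysis plan cannot mask readings already made.

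**Working it through.** **1. Can session be inferred?** Order is the same for all subjects (A.4.5, Exposure; operations plan 2.0). Anyone who sees the date or sequence of a subject's two sessions knows which was air and which CAP. The protocol does not say whether readers see dates.

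**2. Is genotype held before reading?** Yes, by study staff: it steers enrolment (Subject Qualification), may end participation (B.6), and is monitored to keep the null fraction near 40% (A.4.8). Whether the readers are among those staff is not stated.

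**3. Does the study number mask either?** It hides identity. Nothing in A.4.7 removes session, time point or genotype from what a reader receives.

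**4. Is masked reading feasible?**
- Ultrasound: yes. Images are stored and quantified offline.
- Holter: later reading is implied by a recorder worn about 48 hours but is not written. One record may cover both days, so renaming the file would not mask it; the epochs must first be cut out.

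**5. How much latitude is there in HRV?** The epochs are tied to exposure, and chamber entry and exit times are logged (operations plan 2.0). What remains is the looseness of immediately and approximately, a last epoch given as about 24 hours under OUTCOMES but a 10-minute resting measurement at 18 hours in the post-exposure visit, and any beat editing.

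**6. The plan's own figure, used only for scale.** A.4.8 gives N = 15 for a 10% change in HRV, SD 9%, alpha 0.05, power 0.8. The point does not depend on it. Two-sided, a two-sample t test gives 13.7, so 14 per group; a paired t test with SD of differences 9√2 = 12.7 gives 14.75, so 15. The figure is reproduced.

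**7. Illustration with assumed reader shifts.** The documents give no reader error, artery diameter, or planned effect or SD for flow-mediated dilatation.

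*Dilatation.* Percent change = 100 × (peak − rest)/rest. A shift e in the peak frame alone adds 100 × e/rest. With an assumed 4 mm artery:
- e = 0.02 mm: 0.5 points
- e = 0.04 mm: 1.0 point (0.9 to 1.1 points for arteries of 4.5 to 3.5 mm)
- e = 0.08 mm: 2.0 points

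The same shift in both frames nearly cancels. With rest 4.00 and peak 4.24 mm the result is 6.00%; with 0.04 mm added to both it is 0.24/4.04 = 5.94%.

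*HRV.* Suppose no true effect, SD 9, two-sided 0.05 and a constant shift b. Between genotypes (40% of 30 = 12 null, 18 sufficient) the noncentrality is (b/9) × √(12 × 18/30), with 28 df. For CAP against air in 30 pairs it is (b/SD of differences) × √30, with 29 df.

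| Assumed shift b (points) | Genotype, 12 v 18 | CAP v air, SD of differences 9 | CAP v air, SD of differences 12.7 |
|---|---|---|---|
| 0 | 5% | 5% | 5% |
| 1 | 6% | 9% | 7% |
| 2 | 9% | 22% | 13% |
| 3 | 14% | 42% | 24% |
| 4.5 | 25% | 75% | 47% |

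These are false-positive rates if such a shift existed. They do not estimate whether it would.

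**The case against.** **The N/A entry decides nothing about readers.** It stands in a chamber contractor's plan. Section 2.0 of that plan disclaims responsibility for the ultrasound system, and section 3.0 disclaims medical data beyond network storage. This stands: the entry should not be read as a decision by the investigators to leave readers unmasked. What remains is that the IRB application, which describes the measurements, provides no masking either.

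**Reader knowledge is not shown.** A reader might infer that those who read the outcomes know genotype and session. The documents do not say so: no reader is named, and file naming and release are not described. Only study staff are shown to hold genotype. This stands, and limits the point to bias that is possible and avoidable.

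**HRV epochs are not freely chosen.** Also right. It is tempting to describe them as picked after the fact, but OUTCOMES ties them to exposure times. The HRV exposure is therefore the lesser one.

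**The most reader-dependent endpoint is secondary, and its measurement is partly automated.** True, and the primary blood markers are little affected.

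**Masking is more than renaming files.** True for Holter: the chamber log is kept by chamber, so whoever cuts the epochs sees the session. A.4.7 also has abnormal images discussed with the volunteer, which needs an unmasked look. The fix has to allow for both.

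None of this answers the central point that no masking of offline reading is provided where it could be had cheaply.

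**Conclusion.** The point holds as a cheap improvement in design. The protocol provides no masking of outcome reading, session follows from the fixed order, and genotype is held by staff before exposure. Flow-mediated dilatation (secondary) is the endpoint most open to reader bias; HRV (primary) is open to a lesser extent through beat editing and residual latitude in epoch placement.

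The size of the bias cannot be derived from the documents. The figures above rest on an assumed diameter, assumed shifts and, for the paired comparison, an assumed SD of differences. They show only that a shift confined to one session or genotype would pass directly into the contrast. A stronger reading, that the endpoints are biased or that unmasked reading was chosen on purpose, is not supported.

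**What to change.** State in A.4.5, under Brachial artery ultrasound and under OUTCOMES, that exposure delivery is open and offline outcome reading is masked, and bring the Appendix B entry into line. Then specify:

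- **Ultrasound.** Existing data staff give each stored image set a code that carries no date, session, time point or genotype. The sets are quantified in random order by a reader who is not given genotype until the readings are locked.
- **HRV.** Existing unmasked staff cut the 10-minute epochs by a fixed clock rule from the chamber entry and exit log. The rule should also settle the timing of the last epoch. The coded segments then go to the analyst for masked beat editing and analysis.
- **Safety.** Any same-day look at images or ECG stays unmasked and separate from the outcome reading.

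The cost is the coding and segmenting work, a code list, and slightly later ultrasound and HRV results. Subject procedures do not change. The fix does not address the confounding of exposure with order, day and chamber.
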